10.6.2 Statistical Methods for Safety Analyses

Base stage:

Safety and tolerability will be assessed by clinical review of all safety data collected after each study vaccination.

Summary statistics, counts and percentage without confidence interval, will be provided by age group. Proportions of participants with solicited injection-site AEs, solicited systemic AEs within 14 days following study vaccination will be given. Maximum axillary temperatures recorded on the VRC from Day 1 to Day 5 post-vaccination will be summarized.

In addition, proportions of participants with all injection-site and systemic AEs (including solicited and non-solicited AEs) within 30 days following study vaccination, and proportions of participants with SAEs through to Month 7 will also be summarized.

Both Sponsor's criteria (See "Assessment of Intensity" in Section 12.3 Appendix 3) and CFDA's criteria (See Section 12.5 Appendix 5 – Country-specific Requirements) will be applied to assess the intensity of adverse events. The incidence of greatest adverse event intensity reported by a participant based on both the two criteria will be tabulated for: all injection-site AEs and all systemic AEs within 30 days following any study vaccination.

All pregnancy outcomes and infant SAEs will be summarized.

Extension stage:

Summary statistics, including counts and proportion of participants with SAEs during the extension stage will be summarized for 9-19 years old participants.

In addition, pregnancy outcomes and infants SAEs during the extension stage will be summarized.

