10.1 Statistical Analysis Plan Summary

Key elements of the statistical analysis plan are summarized below; the comprehensive plan is provided in Sections 10.2-10.12.

Study Design Overview	A Phase 3 Open-Label Clinical Trial to Study the Immunogenicity, Safety and Tolerability of Recombinant Human Papillomavirus Quadrivalent (Types 6, 11, 16, 18) Vaccine (V501) in Chinese Girls Aged 9-19 Years and Young Women Aged 20-26 Years.
Treatment Assignment	It is a single-arm, open-label study. All enrolled participants will receive a 3-dose regimen of V501. Stratification factors are provided in Section 7.3.1.
Analysis Populations	Immunogenicity: Per protocol immunogenicity (PPI) population Safety: All Participants as Treated (APaT) population

Primary Endpoint(s)	
Base stage:
 
The primary endpoints are cLIA GMTs to each of HPV 6, 11, 16, and 18 at 1 month post dose 3.
 
Extension stage:
 
• cLIA GMTs and seropositivity percentages to each of HPV 6, 11, 16, and 18 at Month 12, Month 24, Month 36, Month 48, and Month 60.• IgG LIA GMTs and seropositivity percentages to each of HPV 6, 11, 16, and 18 at Month 12, Month 24, Month 36, Month 48, and Month 60.
Secondary Endpoints	
Base stage:
 
The key secondary endpoints are cLIA seroconversion percentages to each of HPV 6, 11, 16, and 18 at 1 month post dose 3.
 
Extension stage:
 
Proportion of participants experiencing SAEs.

Statistical Methods for Key Immunogenicity Analyses	
Base stage:
 
The primary hypotheses (H_1) of non-inferiority of GMTs for each of HPV types 6, 11, 16, and 18 will be addressed by 4 one-sided tests of non-inferiority, with $H_0: \text{GMT}_1/\text{GMT}_2 \leq 0.67$ and $H_a: \text{GMT}_1/\text{GMT}_2 > 0.67$, at $\alpha=0.025$. GMT_1 and GMT_2 represent the GMTs at 1 month post dose 3 in girls aged 9-19 years and young women aged 20-26 years, respectively.
 
Extension stage:
 
GMTs and seropositivity percentages to the each of HPV types 6, 11, 16, 18 will be summarized and plotted.

Statistical Methods for Key Safety Analyses	All safety data will be summarized as frequencies and percentages for the two age groups in the base stage and for the 9-19 years old group in the extension stage.
Interim Analyses	No interim analysis is planned.

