10.4.2 Safety Endpoints

Base stage:

Safety endpoints that will be used to evaluate the safety and tolerability of V501 will include proportions of participants who reported solicited injection-site AEs and solicited systemic AEs within Day 1 to Day 15 after study vaccination, and all AEs within Day 1 to Day 31 after study vaccination. In addition, SAEs occurring at any time during the base stage and maximum axillary temperatures reported from Day 1 to Day 5 after study vaccination will be summarized. Pregnancy outcomes and infants SAEs during the base stage will also be summarized.

Extension stage:

SAEs, pregnancy outcomes, and infants SAEs during the extension stage will be summarized.

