The point estimate of seroconversion percentage for a particular HPV type is the ratio of the number of PPI-eligible participants for that particular HPV type who seroconverted to the relevant HPV type over the total number PPI-eligible participants for that particular HPV type who had evaluable Month 7 serology result based on serum sample collected within 31 to 49 days post dose 3.

For each HPV type, the hypotheses to be tested are

$$H_0: p_1 - p_2 \leq -0.05$$

$$H_a: p_1 - p_2 > -0.05$$

where p_1 is the proportion of participants who seroconvert by 1 month post dose 3 in the 9-19 years old group and p_2 is the proportion of participants who seroconvert by 1 month post dose 3 in the 20-26 years old group.

The tests above will be conducted using the method of Miettinen and Nurminen [Miettinen, O. and Nurminen, M. 1985]. The statistical criterion for non-inferiority requires that the lower bound of two-sided 95% confidence interval for the difference (9-19 years old minus 20-26 years old) in seroconversion percentages being greater than -5 percentage points for each HPV type.

Table 4 summarizes the immunogenicity analyses for the base stage.

Table 4 Analysis Strategy for Immunogenicity Variables— Base Stage

Endpoint/Variable (Description, Time Point)	Primary vs. Supportive Approach [†]	Statistical Method	Analysis Population	Missing Data Approach
Primary Objective				
Anti-HPV 6, 11, 16 and 18 cLIA GMTs at Month 7 (each type will be tested separately)	P	Point and 95% CI estimation as well as statistical testing will be performed by using an ANOVA model.	PPI	Observed data only
Anti-HPV 6, 11, 16 and 18 cLIA GMTs at Day 1 and Month 7	S	Point and 95% CI estimation will be provided by using an ANOVA model.	ANPS	Observed data only

Endpoint/Variable (Description, Time Point)	Primary vs. Supportive Approach [†]	Statistical Method	Analysis Population	Missing Data Approach
Secondary Objective				
cLIA % seroconversion to HPV 6, 11, 16, 18 by Month 7 (each type will be tested separately).	P	Point and 95% CI estimation as well as statistical testing of binomial proportion based on Miettinen & Nurminen method	PPI	Observed data only
Anti-HPV 6, 11, 16 and 18 IgG LIA GMTs at Day 1 and Month 7	S	Point and 95% CI estimation will be performed by using an ANOVA model.	PPI	Observed data only
IgG LIA % seroconversion to HPV 6, 11, 16, 18 by Month 7	S	Point and 95% CI estimation based on exact method	PPI	Observed data only

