[†] P=Primary approach; S=Supportive approach.

[‡] Statistical models are described in further detail below:

ANPS = all type-specific naïve participants with serology; CI = confidence interval; GMT = geometric mean titer; PPI = per-protocol immunogenicity.

PBNA results (GMTs and seroconversion percentages) will be summarized as exploratory objective. The PBNA results of the base stage may be summarized in a supplemental report after the data are available.

Extension stage:

Participants in the 9-19 years old group who have completed 3 doses of study vaccination will be followed up to Month 60 to evaluate the persistence of the serum antibody titers for each of HPV 6, 11, 16 and 18 at Month 12, Month 24, Month 36, Month 48, and Month 60. Both cLIA and IgG LIA will be used to measure GMTs and seropositivity percentages.

Table 5 summarizes the immunogenicity persistence analyses for the extension stage.

Table 5 Analysis Strategy for Immunogenicity Variables – Extension Stage

Endpoint/Variable (Description, Time Point)	Primary vs. Supportive Approach [†]	Statistical Method	Analysis Population	Missing Data Approach
cLIA GMTs to HPV 6, 11, 16 and 18 at Month 12, Month 24, Month 36, Month 48, and Month 60	P	Point and 95% CI estimation will be performed by using an ANOVA model; no statistical testing and between group 95% CI will be given.	PPI	Observed data only
cLIA % seropositivity to HPV 6, 11, 16 and 18 at Month 12, Month 24, Month 36, Month 48, and Month 60	P	Point and 95% CI estimation based on exact method; no statistical testing and between group 95% CI will be given.	PPI	Observed data only
IgG LIA GMTs to HPV 6, 11, 16 and 18 at Month 12, Month 24, Month 36, Month 48, and Month 60	P	Point and 95% CI estimation will be performed by using an ANOVA model; no statistical testing and between group 95% CI will be given.	PPI	Observed data only
IgG LIA % seropositivity to HPV 6, 11, 16 and 18 at Month 12, Month 24, Month 36, Month 48, and Month 60	P	Point and 95% CI estimation based on exact method; no statistical testing and between group 95% CI will be given.	PPI	Observed data only
cLIA GMTs to HPV 6, 11, 16 and 18 at Month 12, Month 24, Month 36, Month 48, and Month 60	S	Reverse cumulative distribution curve (RCD) at Month 12, Month 24, Month 36, Month 48, and Month 60	PPI	Observed data only

[†] P=Primary approach; S=Supportive approach.
CI = confidence interval; GMT = geometric mean titer; PPI = per-protocol immunogenicity.

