10.9.2 Sample Size and Power for Safety Analyses

The probability of observing a specific AE in this study depends on the number of vaccinated participants with safety follow-up and the underlying incidence of that specific AE in the study population.

Across six clinical studies, 19 participants out of 3,420 (0.56%) 9-17-year old girls who received V501 reported serious AEs; 0.058% (2 out of 3,420) participants reported serious vaccine-related AEs (MSD data on file).

Assuming that all 383 participants aged 9-19 years enrolled in this study will have safety follow-up, then there is a 88.2% chance of observing at least one serious AE; and 20.1% chance of observing at least one serious vaccine-related AE, on at least one of the 383 participants in the 9-19 years old group. If no serious vaccine-related AEs are observed among the 383 participants in the 9-19 years old group, this study will provide 95% confidence that the underlying percentage of participants with vaccine-related serious systemic AEs is <0.78% (one in every 128 participants) in the 9-19 years old group. This is based on calculation of a 1-sided 95% upper confidence limit of a binomial proportion using exact binomial method of Clopper and Pearson [Clopper, C. J. 1934].

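### Does the base-stage safety analysis need to report the exact upper limit for vaccine-related SAEs that Section 10.9.2 quotes?

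*Combined protocol and SAP*

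**What the plan says.** Section 10.6.2 sets the base-stage safety convention: "Summary statistics, counts and percentage without confidence interval, will be provided by age group". Among the summaries it lists, the one for serious events is that "proportions of participants with SAEs through to Month 7 will also be summarized". Section 10.4.2 defines the matching endpoint as "SAEs occurring at any time during the base stage and maximum axillary temperatures reported from Day 1 to Day 5", again with no causality category. The SAP summary in Section 10.1 agrees in general terms: "All safety data will be summarized as frequencies and percentages for the two age groups in the base stage".

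The confidence statement appears only in Section 10.9.2, on sample size and power for safety. It assumes that all 383 enrolled girls have safety follow-up and then sets a condition: "If no serious vaccine-related AEs are observed among the 383 participants in the 9-19 years old group". Under that condition, "this study will provide 95% confidence that the underlying percentage of participants with vaccine-related serious systemic AEs is <0.78" per cent, or one in 128, by a one-sided exact Clopper-Pearson limit.

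For some immunogenicity percentages that are estimated without a test, the plan does give intervals. The IgG LIA seroconversion row of Table 4 has "Point and 95% CI estimation based on exact method", and the seropositivity rows of Table 5 have "Point and 95% CI estimation based on exact method; no statistical testing and between group 95% CI will be given".

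**The concern.** Taken together, the sections seem not to meet. The only statement about what the study can say on rare serious harm is a confidence limit on vaccine-related SAEs. The methods section rules out confidence intervals, and neither the endpoint list nor the methods section names a vaccine-related SAE count. The 0.78% holds only for zero events in exactly 383 girls. With one event, or fewer girls followed, it would have to be recalculated, and nothing in 10.6.2 says so.

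Section 10.9.2 also words the event in two ways. The condition covers all serious vaccine-related AEs, while the conclusion adds the word systemic, which read literally is narrower.

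Safety in girls is a stated secondary objective. The risk would be a report that gives a bare SAE percentage with no measure of uncertainty, or that repeats 0.78% when its conditions were not met.

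**Working it through.** **Inputs**, all from Section 10.9.2: n = 383 girls; historical SAE rate 19/3,420; historical vaccine-related SAE rate 2/3,420; one-sided 95% exact limit.

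**Reproducing the plan's figures**

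- Upper limit for 0/383: 1 − 0.05^(1/383) = 0.779%, or 1 in 128.3. The plan says below 0.78% and one in 128.
- Chance of at least one SAE: 1 − (1 − 19/3,420)^383 = 88.2%. The plan says 88.2%.
- Chance of at least one vaccine-related SAE: 1 − (1 − 2/3,420)^383 = 20.1%. The plan says 20.1%.

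The arithmetic in 10.9.2 is right.

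**How often the zero-event condition fails.** The expected number of vaccine-related SAEs is 383 × 2/3,420 = 0.22. The binomial probabilities are 79.9% for none, 17.9% for one and 2.2% for two or more. The condition therefore fails with probability 100% − 79.9% = 20.1%, which is the figure the plan already prints.

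**What the limit would then be.** The exact one-sided 95% upper limit for x events in n is the 0.95 quantile of Beta(x + 1, n − x). With n = 383:

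| Vaccine-related SAEs | Upper limit |
|---|---|
| 0 | 0.78% |
| 1 | 1.23% |
| 2 | 1.63% |

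Each value needs only a count and a denominator.

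**The denominator.** Section 10.5.2 admits to the APaT population anyone with at least one dose and some safety follow-up, and Section 9.5.3 requires 30 minutes of observation after every vaccination. The 10% attrition in 10.9.1 concerns evaluability for immunogenicity at Month 7. A girl who leaves before then stays in APaT, so the denominator should be close to the number vaccinated. If it were 364 (an assumed value), the zero-event limit would be 0.82%.

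**The count.** Appendix 3 (Section 12.3) requires an investigator's causality assessment for every AE and SAE, reported on the case report form. The expected number of SAEs of any cause in the girls is 383 × 19/3,420 = 2.1. Splitting about two events by recorded causality needs no new data.

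**The two wordings.** If there are no serious vaccine-related AEs of any kind, there are no systemic ones either. The limit is computed from 0/383 in both cases, so the extra word does not alter the 0.78%.

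**The case for a change.** The strongest case for a change is that the event used to justify the safety sample size ought to be a named output. A reader can compute the exact limit only if the vaccine-related count is reported, and the comprehensive sections do not name it. A bare percentage also says little at these counts: 2/383 is 0.52%, with an exact two-sided 95% interval of 0.06% to 1.87%. The plan uses exact intervals for untested percentages elsewhere, and the cost would be one row and one column.

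Part of this stands. The vaccine-related count is not named in 10.4.2 or 10.6.2, and the wording in 10.9.2 is uneven.

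The rest does not carry to a change.

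- The objectives list the proportion of participants with SAEs as an endpoint, not vaccine-related SAEs, so no stated endpoint lacks an analysis.
- Leaving intervals out of the safety tables is an explicit choice. It fits an assessment made by clinical review with no safety hypothesis.
- The intervals in Tables 4 and 5 belong to stated immunogenicity endpoints (seropositivity is primary in the extension stage) and do not bind the safety convention.
- Interval columns by age group would invite the between-group reading that the plan avoids.
- A conditional planning statement is not made wrong when its condition fails.

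**Conclusion.** No change is needed. Section 10.9.2 says what 383 girls would allow one to exclude if no event occurred; Section 10.6.2 says what will be tabulated. Both can be followed as written, and the first does not commit the sponsor to a table. The gap is one unnamed causality split of about two expected SAEs, plus one superfluous word in 10.9.2 that leaves the 0.78% unchanged. The zero-event condition has a 20.1% chance of failing, and the limit would then most likely be 1.23%. H1, H2, the listed safety endpoints and the success criterion are unaffected.

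This rests on two assumptions. The first is that the study report shows SAEs with their recorded causality, as one would expect from the Section 10.1 statement on all safety data and from the causality field on the case report form. The second is that anyone who quotes the 10.9.2 limit in the report computes it from the observed count and the actual APaT number of girls. If the sponsor prefers to name the count in advance, Section 10 allows non-confirmatory analyses to be updated in a supplemental SAP before database lock.

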10.6.3 Summaries of Baseline Characteristics, Demographics, and other Analyses

Baseline characteristics, demographic variables, medical history, prior and concomitant therapies of the two age groups (9-19 years old vs. 20-26 years old) will be summarized using descriptive statistics or categorical tables. No statistical hypothesis tests will be performed on these characteristics.

The number and percentage of participants screened, allocated, the primary reasons for screening failure, and the primary reason for discontinuation will be displayed.

New medical conditions will be collected during the entire period of the study. The data of new medical conditions will be separately summarized for each base and extension stage.

10.7 Interim Analyses

No interim analyses are planned for this study.

10.8 Multiplicity

Base stage:

For immunobridging primary (H1) and secondary (H2) hypotheses, success is claimed if hypotheses for all 4 HPV types are met. Therefore, no multiplicity adjustment will be made to account for the multiple HPV types. In addition, no multiplicity adjustment will be made between primary and key secondary hypotheses.

Extension stage:

There is no multiplicity adjustment as there is no hypothesis for the extension stage.

10.9 Sample Size and Power Calculations

The sample size of the study is driven by the hypothesis for the base stage. The sample size in the extension stage is based on the number of eligible participants for entering the extension stage.

out using PASS 2008. The minimum criterion for success is that the lower bound of two-sided 95% CI of difference between natural-log-transformed GMTs $> \log(0.67)$. Given the assumed SD of the natural-log-transformed Month 7 titers, this may occur when the observed difference between treatment groups is approximately $\log(0.82)$ or larger.

For the key secondary endpoint, cLIA seroconversion rate, there is an overall 84.2% power to establish that girls aged 9-19 years is non-inferior to young women aged 20-26 years at an overall one-sided, 2.5% alpha-level, if the difference (girls minus young women) in seroconversion rates is greater than -5 percentage points for each HPV type. [Table 7](#) shows the sample size and power calculations for different HPV type under various assumed seroconversion rates for the reference group (young women aged 20-26 years).

The calculations are based on the following assumptions:

1. The participants allocation ratio of 9-19 years old group vs. 20-26 years old group is 1:1;
2. The true seroconversion rates are the same between the two age groups for HPV types 6, 11, 16, and 18;
3. Non-inferiority margin for seroconversion rate is -5%;
4. The cLIA seroconversion rates for young women aged 20-26 years are 98.08%, 98.15%, 98.08% and 98.11% corresponding to HPV 6, 11, 16 and 18 respectively, using the results of China V501-PN030 study;
5. The overall percentages of unevaluable participants are 27.3%, 23.1%, 27.3% and 23.1% for HPV Types 6, 11, 16, and 18, respectively. More specifically, 15%, 10%, 15% and 10% of the participants are initially seropositive to HPV Types 6, 11, 16, and 18, respectively; the expected attrition rate through the Month 7 time point is 10%; the expected percentage of participants excluded due to vaccinations or serology samples out of range is no more than 5%.

Table 7 Sample size and power calculated based on cLIA seroconversion difference in proportion testing

Antigen	Seroconversion rates for young women aged 20-26 years	Enrolled subjects	Effective sample size	Power
HPV 6	98.08%	383	278	0.951
HPV 11	98.15%	383	294	0.966
HPV 16	98.08%	383	278	0.951
HPV 18	98.11%	383	294	0.964
Overall power		0.842 [†]		

[†]Overall power is calculated by multiplying the power for each HPV type.

The estimates of exclusion rates are based on data from previous V501 studies. The calculation is based on an asymptotic method proposed by Miettinen and Nurminen (1985) [Miettinen, O. and Nurminen, M. 1985] and is carried out using PASS 2008. The minimum criterion for success is that the lower bound of two-sided 95% CI of difference $> -5\%$. Given the assumed seroconversion rate of 98% in the 20-26 years old group, this may occur when

the observed difference in response rates is approximately -3% or larger.

10.9.2 Sample Size and Power for Safety Analyses

The probability of observing a specific AE in this study depends on the number of vaccinated participants with safety follow-up and the underlying incidence of that specific AE in the study population.

Across six clinical studies, 19 participants out of 3,420 (0.56%) 9-17-year old girls who received V501 reported serious AEs; 0.058% (2 out of 3,420) participants reported serious vaccine-related AEs (MSD data on file).

Assuming that all 383 participants aged 9-19 years enrolled in this study will have safety follow-up, then there is a 88.2% chance of observing at least one serious AE; and 20.1% chance of observing at least one serious vaccine-related AE, on at least one of the 383 participants in the 9-19 years old group. If no serious vaccine-related AEs are observed among the 383 participants in the 9-19 years old group, this study will provide 95% confidence that the underlying percentage of participants with vaccine-related serious systemic AEs is <0.78% (one in every 128 participants) in the 9-19 years old group. This is based on calculation of a 1-sided 95% upper confidence limit of a binomial proportion using exact binomial method of Clopper and Pearson [Clopper, C. J. 1934].

10.10 Subgroup Analyses

Age group (9-19 years old and 20-26 years old) will be a natural subgroup factor for the base stage. No subgroup analysis will be conducted for the extension stage.

10.11 Compliance (Medication Adherence)

Compliance is defined in this study as receipt of all scheduled study vaccinations. To summarize compliance, the numbers of participants who receive each vaccination will be tabulated. Compliance with the planned vaccination schedule (Day 1, Month 2 and Month 6) will be described by histograms of actual intervals between vaccinations relative to the expected interval.

